## Brief Summary/Abstract

Women with PCOS have decreased GnRH pulse generator sensitivity to suppression by estradiol and progesterone. Increased androgen levels appear to mediate this decrease in sensitivity, as sensitivity can be restored with the androgen receptor blocker flutamide. Adolescent hyperandrogenemia is thought to be a precursor of PCOS, and a subset of adolescent girls with hyperandrogenemia have decreased hypothalamic sensitivity to progesterone similar to their adult counterparts with PCOS. We hypothesize that flutamide will restore hypothalamic progesterone sensitivity in these girls by blocking the effects of androgens. LH (GnRH) pulse frequency will be assessed before and after 7 days of oral estradiol and progesterone in hyperandrogenic adolescent girls who have been pretreated for 14 days with flutamide. The slope of the percentage change in LH pulse frequency as a function of Day 7 progesterone level will be used as a measure of hypothalamic progesterone sensitivity. Hypothalamic progesterone sensitivity in the girls pretreated with flutamide will be compared to hypothalamic progesterone sensitivity in historic controls who did not receive flutamide.

## Background

### *Etiology of PCOS*

Polycystic ovarian syndrome (PCOS) is a common clinical disorder affecting 6-7% of reproductive aged women. PCOS is associated with hyperandrogenism, multiple ovarian cysts, and oligo- or amenorrhea (Stein and Leventhal 1935). It is also a leading cause of infertility. The etiology for PCOS has not yet been elucidated. It has been proposed that hyperinsulinemia, altered ovarian steroidogenesis, and neuroendocrine abnormalities may play key roles either alone or in combination.

### *Neuroendocrine Abnormalities in PCOS*

Neuroendocrine abnormalities, whether primary or secondary, play an important role in PCOS. A group of neurons collectively known as the GnRH pulse generator control the pulsatile secretion of GnRH (gonadotropin releasing hormone) from the hypothalamus. GnRH, in turn, controls the synthesis and secretion of luteinizing hormone (LH) and follicle stimulating hormone (FSH) from the pituitary gland. LH and FSH are both made by the same gonadotrope cell, and which hormone is preferentially synthesized and secreted depends in part on the GnRH pulse frequency. In primates, a GnRH pulse frequency of 1 pulse per hour favors secretion of LH, whereas slower pulses, on the order of 1 pulse every three hours, favor release of FSH. (Wildt 1981). In normally cycling women, the GnRH pulse frequency in the follicular phase is relatively fast, favoring LH secretion. Following the rise in estrogen and progesterone after ovulation, there is a slowing of GnRH pulse frequency, resulting in a decrease in LH and increase in FSH synthesis, which is important for subsequent follicular development. Physiologic doses of exogenous progesterone have been shown to slow LH, and by inference GnRH, pulsatility when given during the follicular phase (Soules et al 1984). Therefore, progesterone plays an important role in regulating the GnRH pulse generator.

PCOS is characterized by persistently rapid LH (GnRH) pulse frequency without the cyclic luteal phase slowing seen in ovulatory women. Our group has shown that women with PCOS have reduced hypothalamic sensitivity

## IRB-HSR#12632: Effect of Androgen Blockade on Sensitivity of the GnRH Pulse Generator to Suppression by Estradiol and Progesterone in Hyperandrogenic Adolescent Girls (JCM021)

to progesterone mediated suppression of LH (GnRH) pulsatility compared to ovulatory controls (Pastor et al 1998). Thus, they require higher plasma progesterone concentrations to achieve the same degree of GnRH suppression. Especially when coupled to the fact that women with PCOS generally have low levels of progesterone secondary to infrequent ovulation, this relative insensitivity contributes to the persistently rapid GnRH pulsatility characteristic of PCOS. The resultant increase in LH leads to augmented ovarian androgen production, while the resultant decrease in FSH leads to impaired follicular development and anovulation. Androgens play an important role in mediating hypothalamic P insensitivity, as P sensitivity can be restored in women with PCOS with the use of the androgen blocker flutamide (Eagleson et al 2000). Thus, in a vicious cycle, hyperandrogenemia promotes neuroendocrine abnormalities that perpetuate hyperandrogenemia.

### *Hyperandrogenemia as a Precursor for PCOS*

Excess androgen production during adolescence is thought to be a precursor of adult PCOS. Women with PCOS often report a history of irregular menstrual cycles during adolescence. A study of girls with menstrual irregularities showed that while some subjects normalized endocrine function as they mature, the majority maintained hyperandrogenism along with the elevated LH levels and polycystic ovaries characteristic of PCOS (Venturoli et al. 1987). Adolescent hyperandrogenemia has also been shown to be associated with higher androgen levels and lower fertility rates in adulthood (Apter and Vihko 1990).

The origin of adolescent hyperandrogenemia is unclear. Along with primary adrenal, ovarian, and neuroendocrine abnormalities, obesity has recently been suggested to play an important role. Several studies have shown a correlation between body mass index (BMI) and androgen levels in adolescent girls. Elevated BMIs are associated with increased total testosterone levels and decreased SHBG levels, leading to marked elevations in free testosterone (Wabitsch et al 1995, Reinehr et al 2005, [name] et al 2006). Androgen levels decrease with weight loss, demonstrating the importance of obesity as a contributing factor (Wabitsch et al 1995, Reinehr et al 2005). The link between obesity and elevated total and free testosterone concentrations is especially concerning in light of the rising incidence of childhood obesity. The most recent data from the National Health and Nutrition Examination Study (NHANES) estimates that 15.1% of girls aged 6-19 years are overweight (defined as BMI  $\geq$  95th percentile on the sex-specific BMI-for-age growth chart) (Hedley et al 2004). Given that obesity is associated with hyperandrogenemia, and adolescent hyperandrogenemia often progresses to adult PCOS, there is concern that the epidemic of childhood obesity may be followed by a rise in the incidence of PCOS.

Similar to women with PCOS, girls with hyperandrogenemia have an increased frequency of LH pulses when compared to age matched controls (Apter et al. 1994). An ongoing study by our group is investigating whether the progesterone insensitivity of the GnRH pulse generator in adult women with PCOS is also seen in adolescent girls with hyperandrogenemia. Analysis of the data to date suggests that the hyperandrogenic adolescent girls have decreased hypothalamic progesterone sensitivity when compared to adolescent controls, with a subgroup (consisting of approximately half of the hyperandrogenic girls) having marked progesterone insensitivity similar to that seen in adult women with PCOS. These data have recently been published (Blank et al. 2009).

Given that androgens mediate hypothalamic progesterone insensitivity in adult women with PCOS, we hypothesize that androgens play a similar role in adolescent girls with hyperandrogenemia and that progesterone sensitivity can be restored with the use of the androgen receptor blocker flutamide.

## IRB-HSR#12632: Effect of Androgen Blockade on Sensitivity of the GnRH Pulse Generator to Suppression by Estradiol and Progesterone in Hyperandrogenic Adolescent Girls (JCM021)

Better understanding the effects of hyperandrogenemia in adolescence and its role in the development of PCOS will hopefully lead to improved prevention and treatment strategies for PCOS. This may prove increasingly important if the current epidemic in childhood obesity results in a growing number of girls with elevated androgen levels.

### Hypothesis to be Tested

We hypothesize that flutamide will restore the sensitivity of the GnRH pulse generator to suppression by estradiol and progesterone in hyperandrogenic adolescent girls. We will compare hypothalamic progesterone sensitivity in hyperandrogenic girls pretreated with flutamide to hypothalamic progesterone sensitivity in historic controls (from JCM010) who did not receive flutamide. The slope of the percent reduction in LH pulses/11 hours as a function of Day 7 progesterone will be used as a measure of hypothalamic progesterone sensitivity.

### Study Design: Biomedical

#### 1. Will controls be used? Yes.

►IF YES, explain the kind of controls to be used. We will use historic controls from 8588/JCM010. 8588/JCM010 is identical to this study, except flutamide was not given. Therefore, it will allow us to compare the hypothalamic progesterone sensitivity data from hyperandrogenic adolescent girls in the presence and absence of flutamide.

#### 2. What is the study design?

This study is not blinded.

#### 3. Does the study involve a placebo? No.

### Human Participants

**Ages** 13-18 years

**Sex** Female

**Race** All races will be recruited and enrolled.

**Subjects- see below**

#### 1. Provide target # of subjects (at all sites) needed to complete protocol to obtain statistically significant results.

13

#### 2. Describe expected rate of screen failure/ dropouts/withdrawals from all sites.

In a similar study (JCM010), we have historically obtained complete, usable data in approximately 65% of the subjects who enrolled in the study. However, that study did not involve taking flutamide. Because of the additional demands associated with taking flutamide and coming in for additional blood draws for LFT monitoring, as well as the possibility that some participants may develop mild LFT abnormalities and therefore be forced to stop the study, we suspect that the screen failure/dropout rate will approach 50%. Therefore, we plan to enroll 26 subjects, with a goal of obtaining complete, usable data in 13.

**IRB-HSR#12632: Effect of Androgen Blockade on Sensitivity of the GnRH Pulse Generator to Suppression by Estradiol and Progesterone in Hyperandrogenic Adolescent Girls (JCM021)**

- 3. How many subjects will be enrolled at all sites? 26**
- 4. How many subjects will sign a consent form under this UVa protocol? 26**

## **Inclusion/Exclusion Criteria**

**1. List the criteria for inclusion**

- Girls ages 13 to 18
- Tanner IV or V stage of puberty
- Post-menarche
- Hyperandrogenemic (total testosterone > 0.4 ng/mL or free testosterone > 35 pmol/L) with or without hirsutism
- Normal AST/ALT (AST  $\leq$  35 U/L, ALT  $\leq$  55 U/L)
- Hemoglobin  $\geq$  11.0 g/dL for African American subjects; Hemoglobin  $\geq$  11.5 for non-African American subjects
- Normal screening labs (with exception of the expected hormonal abnormalities inherent in hyperandrogenemia)
- Sexually active subjects must agree to abstain or use double barrier contraception during the study  
Subjects must agree not to take any other medications during the course of the study without approval by the study investigators

**2. List the criteria for exclusion**

- Abnormal screening labs (with the exception of the expected hormonal abnormalities inherent in hyperandrogenemia)
- Elevated AST/ALT (AST > 35 U/L, ALT > 55 U/L)
- Hemoglobin < 11.5 g/dL for non-African American subjects; Hemoglobin < 11.0 g/dL for African American subjects
- Weight < 32 kg
- History of liver disease, peanut allergy, deep venous thrombosis, breast cancer, endometrial cancer, or cervical cancer
- Pregnant or breast feeding
- On medications known to affect the reproductive axis within 3 months of the study (including oral contraceptive pills, metformin, and spironolactone)
- On medications known or likely to inhibit or induce CYP1A2 or CYP3A4 (please see “Restrictions on use of other drugs or treatments” section below for common examples of such drugs)
- Are currently participating in another study or have been in one in the last 30 days.

**3. List any restrictions on use of other drugs or treatments.**

Subjects must not take medications known to affect the reproductive axis (including oral contraceptives, metformin, and spironolactone) for 90 days prior to and during the study.

Flutamide is a substrate of CYP1A2 and 3A4 and it inhibits CYP1A2 (weak). Thus, CYP1A2 and 3A4 inducers/inhibitors may not be used for one month prior to and during the use of flutamide. [CYP1A2 inducers

## IRB-HSR#12632: Effect of Androgen Blockade on Sensitivity of the GnRH Pulse Generator to Suppression by Estradiol and Progesterone in Hyperandrogenic Adolescent Girls (JCM021)

(e.g., aminoglutethimide, carbamazepine, phenobarbital, and rifampin) may decrease the levels/effects of flutamide; CYP1A2 inhibitors (e.g., amiodarone, ciprofloxacin, fluvoxamine, ketoconazole, lomefloxacin, ofloxacin, and rofecoxib) may increase the levels/effects of flutamide; CYP3A4 inducers (e.g., aminoglutethimide, carbamazepine, nafcillin, nevirapine, phenobarbital, phenytoin, and rifamycins) may decrease the levels/effects of flutamide; CYP3A4 inhibitors (e.g., azole antifungals, ciprofloxacin, clarithromycin, diclofenac, doxycycline, erythromycin, imatinib, isoniazid, nefazodone, nicardipine, propofol, protease inhibitors, quinidine, and verapamil) may increase the levels/effects of flutamide; warfarin effects may be increased by use of flutamide.]

### Bio-statistical Analysis-GCRC

#### 1. What are your plans for the statistical analysis?

The primary outcome variable for the study is the slope of the percent change in LH pulses as a function of day 7 progesterone level. The comparison will be made between the participants in this study (all of whom receive flutamide) and historical controls from study 8588/JCM010. The historical controls will be the Tanner 4-5, hyperandrogenic girls who have completed 8588/JCM010. Study 8588/JCM010 involves an assessment of hypothalamic progesterone sensitivity identical to that in this study. The only difference in the studies is that girls in this study are treated with flutamide before and during the assessment of hypothalamic progesterone sensitivity while those in 8588/JCM010 are not. Based on a similar study in adults (Eagleson et al 2000), we hypothesize that the use of flutamide will normalize hypothalamic progesterone sensitivity in hyperandrogenic adolescent girls. The power calculations were based on data from 8588/JCM010 in which Tanner 4-5 hyperandrogenic girls have a slope of 1.8, while Tanner 4-5 normal controls have a slope of 9.5. The pooled SD for these two groups was 6.6. Using this data, we determined that we would need a sample size of 13 subjects in this study (to be compared with 13 historical controls from 8588/JCM010) in order to achieve a statistical significance with a power of 80% and Type 1 error rate of 0.05. This power calculation was performed based on an expected slope difference of 7.7 between the participants in this study and the historic controls. Given the historical dropout/withdrawal rate for 8588/JCM010 of 65% and the additional demands of this study secondary to the addition of flutamide, we anticipate a dropout/withdrawal rate of around 50%. Therefore, we propose enrolling up to 26 girls with the goal of obtaining complete, analyzable data in 13.

Given the relatively small number of subjects to be studied, we anticipate the need to use non-parametric testing. Therefore, the primary comparison will be performed using the Wilcoxon Rank Sum test. A p-value of <0.05 will be considered significant.

#### 2. What is the primary outcome variable upon which a sample size estimate is based?

The slope of the percent change in LH pulses as a function of Day 7 progesterone.

#### 3. Do you have an adequate sample size, or is my sample size larger than necessary?

We calculated that we will need a sample size of 13 subjects in this study (to be compared with 13 historical controls from 8588/JCM010) in order to achieve a statistical significance with a power of 80% and Type 1 error rate of 0.05. Given the historical screen failure/dropout/withdrawal rate for 8588/JCM010 of 65% and the additional demands of this study secondary to the addition of flutamide, we anticipate a screen failure/dropout/withdrawal rate of around 50%. Therefore, we propose enrolling

## IRB-HSR#12632: Effect of Androgen Blockade on Sensitivity of the GnRH Pulse Generator to Suppression by Estradiol and Progesterone in Hyperandrogenic Adolescent Girls (JCM021)

up to 26 girls with the goal of obtaining complete, analyzable data in 13. We believe this sample size is adequate and not excessive.

### Biomedical Research

#### 1. What will be done in this protocol?

All procedures performed in this protocol are being done solely to answer a research question and generate generalizable knowledge.

#### Outpatient Consent and Screening

After a potential subject is identified, we will arrange for her to come to the CRU or alternate UVA clinical unit for an outpatient consent and screening exam. The goals and procedures of the study will be explained to the potential subject and her parents, and they will be given the opportunity to ask any questions. The potential subject and her parents will be asked to sign the assent and consent forms. A physician will record a family and personal medical history and perform a physical exam. Subjects will need to fast for a minimum of 8 hours prior to screening blood draw. Blood will be drawn for screening tests (CBC, Chem 17 including LFTs, prolactin, LH, FSH, E1, E2, P, total T, androstenedione, 17-OHP, DHEA-S, fasting insulin, Insulin-like Growth Factor 1 (IGF-1), glucose, SHBG, TSH, hCG, cholesterol, LDL, HDL, and a number of cytokines and adipokines, including adiponectin, leptin, resistin, PAI-1, IL-1b, IL-6, IL-8, TNFa, MCP-1, HGF and NGF.) In the rare event that a subject has an elevated follicular phase 17-OHP on screening, she will be referred to her physician for further evaluation, including cortrosyn stimulation test to rule out congenital adrenal hyperplasia. She will only be able to continue in the study if she has a documented normal 17-OHP response to cortrosyn stimulation. Potential subjects must fall within the normal range on all blood tests to be admitted to the study, except for hyperandrogenemic girls who will be expected to have some abnormal hormone levels.

Subjects will be administered 1 month of iron supplementation following screening, provided their screening labs show they are eligible to participate in the study. As soon as screening lab results are available, and subjects are found to be eligible for study participation, subjects weighing  $\leq$  38 kg will be given 1- 325 mg tablet a day and subjects weighing  $>38$  kg will be given 2- 325 mg tablets a day. The first overnight admission may occur anytime within this 30 day period or after the 30 day period. Subjects will be given the option to pick up this supply of iron in the Clinical Research Unit or have it mailed to them.

Note: Subjects who have just completed IRB-HSR# 8588/ JCM010 will be allowed to consent for JCM021 8 weeks after completing JCM010 (IRB-HSR# 8588). In addition, screening laboratory results from JCM010 (ie. CBC, Chem 17 including LFTs, prolactin, LH, FSH, E1, E2, P, total T, androstenedione, 17-OHP, DHEA-S, fasting insulin, glucose, TSH, hCG, cholesterol, LDL and HDL) may be used as the baseline screening results for this study unless  $> 3$  months have occurred between completion of JCM010 and enrollment in JCM021. If  $> 3$  months have occurred between completion of JCM010 and enrollment in JCM021, then subjects will need to complete all of the screening labs for JCM021. Subjects enrolling in JCM021 8-12 weeks following completion of JCM010 will have blood drawn for a comprehensive metabolic panel and pregnancy test, and may begin flutamide administration immediately upon confirmation that the AST/ALT is within the normal range and the pregnancy test is negative.

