
### **Day 1: Start Estradiol and Progesterone**

Starting the day of discharge from the first inpatient admission, subjects will be given oral estrogen (estrace, 0.5-1 mg once a day) and oral progesterone suspension (20 mg/ml, 25-100 mg) three times a day at 0700, 1500, and 2300 hr for seven days. If the 1500 dose is incompatible with school schedules, alternative dosing schedules can be arranged. Generally this will entail taking the afternoon dose immediately upon returning home from school without any change in the morning and evening dosing times. Dosages will be based on weight. The target mean plasma progesterone concentration is 2-8 ng/dL. Each subject will be

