**4. Do you plan to ask the subjects to do anything for the study prior to signing a consent? yes**

Subjects will be asked to fast (nothing to eat or drink except water after midnight) prior to the screening visit. Subject will be advised that only individuals who have taken no hormonally-active medications for 3 months prior to the study will be eligible for participation. Subject will be advised to consult her personal physician prior to stopping any medications.

\*\* Request waiver of documentation of consent for minimal risk screening procedures\*\*

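### Does the 8-week entry route for JCM010 completers conflict with the 3-month washout in a way that affects the analysis?

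*Combined protocol and SAP*

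**What the plan says.** The note closing Outpatient Consent and Screening deals with girls coming from JCM010. They "will be allowed to consent for JCM021 8 weeks after completing JCM010". Those who enrol at 8-12 weeks have a metabolic panel and a pregnancy test. They "may begin flutamide administration immediately upon confirmation that the AST/ALT is within the normal range", provided the pregnancy test is also negative. JCM010 screening results may serve as baseline unless more than 3 months have passed.

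Three other places set a drug-free period:

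- The exclusion criteria bar girls "On medications known to affect the reproductive axis within 3 months of the study". A separate exclusion concerns earlier research: "Are currently participating in another study or have been in one in the last 30 days".
- Item 3 of the same section, on other drugs and treatments, bars reproductive-axis drugs ("including oral contraceptives, metformin, and spironolactone) for 90 days prior to and during the study").
- In the Recruitment and Consenting appendix, item 4, candidates are told before the visit that "only individuals who have taken no hormonally-active medications for 3 months prior to the study will be eligible for participation".

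On JCM010 itself, Study Design item 1 states that "8588/JCM010 is identical to this study, except flutamide was not given". Its completers therefore had the Day 1 regimen, in which "subjects will be given oral estrogen (estrace, 0.5-1 mg once a day) and oral progesterone suspension" for seven days.

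**The concern.** Estradiol and progesterone plainly act on the reproductive axis; the trial rests on that. The drugs named in the washout sections are given as examples, so the list is open. Read literally, a girl who took these hormones in JCM010 less than 90 days ago is barred by three sections and admitted by a fourth, and the note that admits her is not worded as an exception. The term for completing JCM010 is also undefined: it could mean the last hormone dose or a later follow-up visit.

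The Day 0 LH sampling is the baseline for the percent change in pulse frequency, and so for the primary slope. If a recent hormone course still influenced that baseline, some flutamide girls would enter the comparison in a state that the general washout is meant to prevent. Two members of staff applying different sections could also reach different eligibility decisions for the same girl.

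**Working it through.** **Plan's own figure.** The plan computes nothing from the interval. Its sample size does reproduce: difference 9.5 − 1.8 = 7.7, SD 6.6, 80% power, 0.05 (two-sided assumed; the plan does not say) gives 12.57 per group by a two-sample t-test, so 13; and 13 / (1 − 0.5) = 26 enrolled. The interval since JCM010 is not an input to either number.

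**Inputs for the day count.** Entry window 8 to 12 weeks and immediate flutamide start (Outpatient Consent and Screening, note). Day 0 is 14 days after flutamide starts (Day Minus 14). Washout 90 days (restrictions on other drugs). Lag from last hormone dose to completion: 0 days, or 14 days if JCM010 had a visit like this protocol's Day 21 draw. The 14 is an assumption, because the JCM010 protocol is not part of the documents.

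**Formulae.** Days to flutamide = 7 × weeks + lag. Days to Day 0 = that + 14.

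| Entry | Lag | To flutamide | Against 90 | To Day 0 | Against 90 |
|---|---|---|---|---|---|
| 8 weeks | 0 | 56 | −34 | 70 | −20 |
| 8 weeks | 14 | 70 | −20 | 84 | −6 |
| 12 weeks | 0 | 84 | −6 | 98 | +8 |
| 12 weeks | 14 | 98 | +8 | 112 | +22 |

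With an immediate start, entry at 8 weeks is under 90 days on all four readings; entry at 12 weeks is under on one of four.

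**Usual scheduling.** The Consenting Process text says that girls generally begin the main part 1-2 months after screening. Taking a month as 30 days and flutamide as the beginning of the main part, the 8-week entrant with no lag reaches flutamide at 56 + 30 = 86 to 56 + 60 = 116 days, and Day 0 at 100 to 130. The gap then nearly disappears (4 days short at worst, and only at flutamide start). The immediate start is still permitted, so the table remains the limiting case.

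**Reading the sections together.**

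1. Suppose that JCM010 hormones count and the interval runs from last dose to flutamide start. The latest point of the 8-12 week pathway is 12 × 7 = 84 days, below 90, so no girl could start at once under the note's permission. A reading that empties a paragraph written for these girls is the less natural one.
2. The restriction on other drugs applies before and during the study. The study itself gives estradiol and progesterone from Day 1, so that rule cannot literally include study-supplied hormones.
3. The named examples are ordinary prescriptions, and the pre-visit advice goes on to mention consulting a personal physician before stopping medication. Both suggest outside treatment.
4. Earlier research participation has its own 30-day rule, which 56 days satisfies.

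**Link to the analysis.** Bio-statistical Analysis item 1 compares girls with complete, usable data against JCM010 controls by the Wilcoxon rank-sum test. The washout does not define that set. A sensitivity run without girls under 90 days, counted from last dose to Day 0, would remove only immediate-start entries from 8 to (90 − 14) / 7 = 10.9 weeks. The documents do not say how many there are, and there may be none.

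**The case for a change.** The strongest case for a change is that the overlap is a live route into a very small group. JCM010 completers from the past year are contacted by letter, and with 13 analysable girls each one is 1/13, about 8%, of the flutamide group. The short pathway has no new hormone measurement before flutamide, only the metabolic panel and pregnancy test. The pre-visit advice refers broadly to hormonally active drugs, and the Day 21 section describes the trial's own agents as hormonal. A sentence of clarification and one derived date would cost almost nothing.

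Much of this stands as a remark on drafting. The exemption is not written down, and the pre-visit advice is the hardest text to square with the note.

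It does not establish a statistical defect. The exposure is a seven-day course ending at least 56 days before flutamide and 70 days before Day 0, and the documents give no size or direction for any residual effect. Estradiol and progesterone are measured every 2 hours at Day 0, so residual circulating hormone could be looked for, although that would not settle every kind of after-effect. The sensitivity run would adopt one of the disputed limits as its cut-off and thin a group of 13, to address a carry-over that nobody has shown.

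**Conclusion.** The concern does not call for a change to the plan. The sections do differ: an 8-week entrant who starts at once is 34 days short of 90 at flutamide start and 20 short at Day 0 if completion means the last dose, or 20 and 6 short if completion is a visit 14 days later. By 12 weeks the shortfall is 6 days on one reading and absent on the other three.

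This is an unwritten exemption or definition that staff can fill from the text. The note is specific to JCM010 completers, and the washout reads most naturally as covering outside medication. Following the note as written is not shown to give a wrong or worse result. The analysis set, the primary test and the sample size of 13 do not depend on the interval. The four sections must be reconciled in wording by the sponsor; which interval is right is a clinical matter on which nothing is said here.

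The conclusion rests on JCM010 having used the same hormone course, as the protocol states, and on the supplied text alone: the consent pages are not available. The counts with a 14-day lag rest further on an assumed JCM010 visit. Evidence of carry-over at these intervals, or a large number of immediate-start re-entrants, would reopen the question.
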